5.4.2 Exclusion Criteria

- 231 Exclusion criteria are systemic infection, immunosuppressive disorder, implanted electronic devices,
- pregnancy, previous allergy to skin contact materials and/or anesthetic agent altered mental status, inability
- 233 to provide consent, greater than 180 morphine equivalents (MED) per day.

234 5.5 Study Plan

- The study includes 13 Visits. Please refer to the Appendix for a schedule of study procedures for both
- 236 groups as well as outcomes measured at each visit.
- Patients planned for nontraumatic TFA or TTA will be screened by the study investigators who are working
- on the Acute Pain Service (APS). APS is usually consulted for all transferoral and transtibial amputations
- 239 to provide perioperative anesthesia, which typically includes placement of a peripheral nerve catheter for
- local anesthetic blockade. When a potential subject is identified, study investigators will begin a chart
- review for screening purposes. The investigators will review the medical record of potential subjects and
- complete Form 00 (Screening and Demographic Information). Chart review will include the collection of
- name, social security number and date of birth from CPRS, the ORC, and the Vascular Clinic. Protected
- Health Information (PHI) will be used to locate and review appropriate medical records (CPRS and paper
- medical records) to determine study eligibility. If a subject appears to meet all eligibility criteria (see
- 245 incident records) to determine study engionity. If a subject appears to ineet an engionity enterta (see
- Section 5.4. Eligibility), then he/she will be contacted by study investigators and given recruitment
- 247 materials detailing study objectives, randomization, procedures, follow-up encounters, assessments, and
- 248 potential risks and benefits. The subject will be provided with patient information pertaining to the
- 249 peripheral nerve stimulator system under investigation. If permitted by the subject, a sponsor representative
- or their designee may be present at any of the study visits to advise on material handling and answer
- questions as needed.

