Patients who are interested in participation will be asked to complete a Beck Depression Inventory (see Form BDI) to be screened for depression (must score 20 or less) prior to enrollment. Veteran participants who are evaluated by study staff and suspected to be depressed will be further evaluated by a psychiatrist or psychologist utilizing the Mental Health Consultation and Liaison Service at McGuire VAMC. Research study staff will page the C&L service at [name] (Use [name] after 4pm and on weekends) and then walk the participant to the C&L provider to facilitate the evaluation on the day that the participant

presents as depressed. If non-veterans participants are enrolled, arrangements made for him/her to be evaluated at a non-VA facility.

[figure not shown]

Figure 1 Subject flowchart.

258

259

260261

Patients who agree to participate in the study will be asked to sign the Consent Form. Ideally, patients should provide informed consent and be enrolled in the study prior to surgery. Typically, the local anesthetic peripheral nerve block catheters (or single shock femoral or sciatic nerve blockade) are placed on the day prior to surgery or day of surgery. Subjects will be given the opportunity to enroll in the study when the catheter is placed, however, those who wish to decide on enrollment after their surgery may be enrolled up until the time in which their peripheral nerve block catheter is removed, which is usually by post-op day 5. Upon enrollment, subjects will be evaluated by APS daily.

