6.2 Sampling and Randomization Procedures

Based upon historical data on amputations at the HHM-VAMC, there are estimated to be one to two 474 475 amputations per week that would qualify for enrollment in this study. Subjects will be screened for enrollment through the vascular surgery clinic. A considerable proportion of vascular clinic patients will 476

require lower extremity amputation and are usually scheduled for next day surgery due to the urgency of 477

presentation. Study investigators will conduct a chart review of potential subjects and complete Form 01-478

479 A (screening and demographic information). Based on the chart review, if a patient appears to meet all 480

eligibility criteria, then they will be contacted by study investigators for potential enrollment. If the patient

agrees to participate, they will be consented and randomized to Group 1 or Group 2. 481

482 Prior to the start of this study, a member of the study staff that is not involved with recruitment or data

483 evaluation will be responsible for generating a random string of group assignments long enough to fill all

anticipated spots in this study. The numbers will be placed in secure envelopes by blocks of two. A block 484

485 of two will contain one assignment to the Treatment Group and one assignment to the Control Group. As

486 subjects are consented and enrolled in the study, they will be assigned an envelope which randomizes them

487 to a group. Subjects are not blinded to their group assignments. Subjects in the Treatment Group will

receive the investigational treatment (30 to 60-days of peripheral nerve stimulation) in addition to SMT. 488

489 Subjects in the Control Group will be treated with the SMT alone.

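### Fixed blocks of two, printed in the protocol of an unblinded pilot, make 8 of 16 assignments certain in advance if envelopes are used in block order and the team knows the previous arm

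*Combined protocol and SAP*

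**What the plan says.** Section 6.2 has a staff member who takes no part in recruitment or data evaluation prepare the assignments before the study starts. It then says "The numbers will be placed in secure envelopes by blocks of two" and that each block "of two will contain one assignment to the Treatment Group and one assignment to the Control Group". No other block size is mentioned. The Sample Size text in section 6.0 gives 16 subjects, 8 per group.

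On timing, 6.2 says that a patient who "agrees to participate, they will be consented and randomized to Group 1 or Group 2", and that as "subjects are consented and enrolled in the study, they will be assigned an envelope which randomizes them" to a group. It does not say that envelopes are numbered, opaque or opened in a fixed order, or that block details are withheld from recruiters.

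On who knows what, 6.2 states "Subjects are not blinded to their group assignments", and section 3.2 gives the control group standard therapy alone, with no sham. Under 5.5, "Patients planned for nontraumatic TFA or TTA will be screened by the study investigators who are working" on the Acute Pain Service, and "Upon enrollment, subjects will be evaluated by APS daily". Study investigators contact candidates (6.2), place leads (5.6) and see both groups every day in hospital (5.5.3).

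On the consent window, 5.5 prefers consent before surgery, but "those who wish to decide on enrollment after their surgery may be enrolled up until the time" the nerve block catheter comes out, usually by postoperative day 5.

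**The concern.** In a block of two the first assignment fixes the second. Treatment is visible because one arm has a lead placed and the other does not. Anyone who has read 6.2 and knows the arm of the pair's first subject therefore knows what the next envelope holds. An independent list-maker and secure envelopes protect the list from being read, but not from being deduced.

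Foreknowledge could affect whom the team approaches and when it seeks consent. If the envelope is opened only after surgery, it could also affect how the moderate-pain condition in 3.2 is judged; that condition is not among the inclusion criteria in 5.4.1. There is room for choice: 6.2 estimates one to two qualifying amputations a week, about 4 to 9 a month (52/12 = 4.3 weeks per month), while the plan expects to enroll 2 to 4 a month. Refusals may explain some of that gap.

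At stake are the between-group pain comparisons in 4.1, which are self-reported and analysed by two-sample t-test (6.3). With 8 per arm, one steered patient is 1/8 = 12.5% of an arm. Comparing within-subject changes (6.3) would offset only part of any bias. The screening record in 8.2 might help detect it but would not prevent it. Feasibility and safety aims are largely unaffected, although 1.2 and 6.0 name randomization among the procedures this pilot is meant to test and refine.

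**Working it through.** **Inputs.** 16 subjects, 8 per arm (6.0, Sample Size); blocks of two, one of each arm (6.2); 2 to 4 enrollments per month (study-duration paragraph just before 6.0). The plan's own figures agree: 16/2 = 8 complete blocks, giving 8 per arm.

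**Method.** Exact enumeration of all possible sequences. Unless stated otherwise, the guesser knows the scheme and all past assignments. An assignment is certain when only one arm is possible. A guess is the likelier arm, or a coin toss when both are equally likely.

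**Plan as written** (256 sequences, previous arm always known). Certain: 8 blocks × 1 = 8 of 16. Correct guesses: 8 + 8 × 0.5 = 12 of 16 (75%). Simple randomization would give 0 certain and 8 correct.

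**Previous arm known for only a fraction q of second assignments.** Certain = 8q; correct = 8 + 4q. At q = 0.5 this gives 4 certain and 10 correct (63%).

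**Envelopes drawn from one mixed stack rather than in block order** (12,870 sequences). Certain = 16/9 = 1.78; correct = 10.05.

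**Known at the time of consent.** Assume random arrivals at r per month and a lag of L days between consent and opening the envelope. The expected number of the 8 second assignments already known when the next patient consents is 8 × exp(−L × r/30). The lags are illustrative; the documents do not give one.

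| Lag (days) | r = 2 | r = 4 |
|---|---|---|
| 0 | 8 | 8 |
| 1 | 7.48 | 7.00 |
| 2 | 7.00 | 6.13 |
| 8 | 4.69 | 2.75 |

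Section 6.2 ties the envelope to consent. Section 3.2 describes enrollment and randomization 2 to 7 days after surgery, which does not itself establish a lag. The Appendix schedule appears to place randomization at Visit 1, but the table is too damaged in the available text to settle this.

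**Alternatives for the same 16 subjects.**

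| Scheme | Certain | Correct guesses | Split after 8 subjects |
|---|---|---|---|
| Blocks of two | 8 | 12.0 (75%) | always 4:4 |
| One permuted 8:8 list | 1.78 | 10.05 (63%) | 6:2 or worse 1698/12,870 = 13.2%; 7:1 or worse 130/12,870 = 1.0%; 8:0 in 2/12,870 |
| Blocks of 4, 6, 6 in random order | 2.58 (sizes known) or 1.44 (only 8 per arm known) | 11.03 (69%) | 4:4 62.2%; 5:3 37.8%; arms never more than 3 apart |

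**Keeping the pairs but hiding them.** If only 8 per arm is known, just the 16th assignment is certain (1.0). But always guessing the arm that is behind needs no knowledge of the block size and still gets 12.0 right, against 10.05 for the single list and 11.03 for 4/6/6.

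**The case against.** The figure of 8 of 16 is a maximum resting on conditions the protocol does not state: use in block order, and knowledge of the previous arm. The overlap between recruiting and treating is shown for the team, not for any one person. If the previous arm is known half the time, pairs are no more guessable (10 of 16) than the single list under full knowledge. Patients are usually scheduled for surgery the next day (6.2), most entry criteria are objective, and opening the envelope before surgery would rule out influence through the moderate-pain condition. Hiding the pairs alone cuts the certain count from 8 to 1.0. The follow-on trial is described in 1.2 as blinded and placebo-controlled, so earlier arms would be harder to know there. Pairs keep the arms balanced at any stopping point.

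Much of this stands as a limit on size. The conditions are assumptions, though likely ones: there is no sham, the same team recruits and treats, and enrollments are spaced over weeks. Printed here means printed in the protocol the investigators hold; nothing shows that it was public during recruitment. Urgency and objective criteria narrow the discretion, but whom to approach and when to seek consent remain open. Hiding the pairs helps on certainty, but leaves the simple guess at 12 of 16 and may be undone as staff notice the alternation. None of this gives a reason to keep the pairs when a less predictable list costs almost nothing.

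**Conclusion.** The concern holds and should be fixed. With envelopes used in block order and the previous arm known, exactly 8 of 16 assignments are certain in advance and 12 of 16 are guessable on average. If either condition holds only partly, the figures fall: 4 certain and 10 guessable with half of the previous arms known, 1.8 and 10.0 with a mixed stack. At an illustrative 8-day lag, 2.8 to 4.7 of the 8 second assignments are known at consent. The counts assume complete blocks and no replacements. This is a weakness in allocation concealment that permits selection bias in the primary pain comparisons. It is not evidence of bias, and the documents give no basis for estimating how large any bias would be.

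**What to change.** Before the list is generated:

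- Delete from 6.2 the reference to blocks of two and the sentence on block content. State only that allocation is 1:1 by a restricted random list whose details are kept in a separate randomization file, not available to staff who recruit, consent, treat or assess subjects.
- State in 6.2 that assignments are in sequentially numbered, opaque, sealed envelopes opened in number order.
- In the separate file, specify one permuted list of 8 Treatment and 8 Control. If balance during accrual matters more, use one block of 4 and two of 6 in random order, which is the smaller gain (69% guessable against 75%).
- If replacements are anticipated, add a spare permuted block of 2 and 2 after the 16th envelope. Of its 4 assignments, 1.33 are certain on average if its size is known.
- Reconcile 3.2, 6.2 and the Appendix on when the envelope is opened.

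The cost is small: one list made once, a separate file and perhaps a few spare envelopes, with no added patients. The downside is temporary imbalance, or unequal arms if the trial stops early, with the probabilities tabulated above. Pairs avoid that and extend to replacements without a spare block.

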3.2 Study Design

- This prospective randomized controlled trial aims to assess the feasibility of using a novel percutaneous
- peripheral nerve stimulator system to produce clinically significant reductions in acute post-surgical pain
- after nontraumatic lower extremity amputation, and evaluate reductions in the incidence and/or severity of
- chronic PLP or RLP. Subjects who have moderate pain 2 to 7 days after transfemoral or transibial
- amputation surgery will be enrolled and randomized to Group 1 ("Treatment Group") or Group 2 ("Control
- Group"). Subjects in Group 1 will be treated with 30 to 60 days of PNS in addition to SMT. Subjects in
- Group 2 will be treated with the SMT alone. SMT is defined as the same routine medical care given to all
- patients, regardless of whether they are enrolled in the study. This may include, but is not limited to non-
- opioid and opioid pain medications, regional anesthesia peripheral nerve blockade, daily postoperative
- visits by the Acute Pain Service, and follow-up appointments in the Interventional Pain Clinic.
- Group 1: 30 to 60 days of peripheral nerve stimulation starting within 7 days after surgery and Standard Medical Therapy
 - Group 2: Standard Medical Therapy only
- Subjects are evaluated daily by study investigators from the time of study enrollment to hospital discharge.
- 30 Subsequent telephone or outpatient clinic evaluations occur at intervals which are detailed in the Schedule
- of Study Procedures (Appendix).

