5.4 Eligibility

5.4.1 Inclusion Criteria

Inclusion criteria are nontraumatic transfemoral or transtibial amputation (TFA or TTA, respectively) and age over 18..

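### Section 6.2 randomizes at consent but the Appendix randomizes at Visit 1, and the moderate pain named in 3.2 is never applied; unblinded subjects may know their arm before the self-reported baseline

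*Combined protocol and SAP*

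**What the plan says.** **Time of randomization.** Section 6.2 ties randomization to consent twice. A patient who "agrees to participate, they will be consented and randomized to Group 1 or Group 2" is one statement. The other is that as "subjects are consented and enrolled in the study, they will be assigned an envelope which randomizes them" to a group. Section 5.5 sets the time of consent: "Ideally, patients should provide informed consent and be enrolled in the study prior to surgery". Those who decide later "may be enrolled up until the time in which their peripheral nerve block catheter is removed, which is usually by post-op day 5". Section 5.5.1 places Visit 1 at least 24-48 hours after that removal, or after a single-shot block has worn off. The Appendix marks Randomize in the Visit 1 (Baseline) entry and not in the Screen and Consent entry.

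**Pain condition.** Section 3.2 reads "Subjects who have moderate pain 2 to 7 days after transfemoral or transibial" and continues "amputation surgery will be enrolled and randomized to Group 1" or Group 2. Section 5.4.1 reads "Inclusion criteria are nontraumatic transfemoral or transtibial amputation (TFA or TTA, respectively) and age over 18". The exclusions in 5.4.2 set no pain level. Section 5.5 adds a depression-score limit only. Visit 1 records pain but sets no threshold for continuing.

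**Blinding and analysis.** Section 6.2 states: "Subjects are not blinded to their group assignments". Section 6.3 compares changes in pain between groups and does not name the reference value.

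**The concern.** In an unblinded trial with self-reported pain, baseline should be recorded before the subject can learn the arm. Otherwise hope or disappointment about the allocation can enter the baseline itself, and a change score carries that into the treatment comparison. Under 6.2 the allocation comes first. Under the Appendix it comes at the baseline visit, although the Appendix gives no order of forms and randomization within that visit.

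The pain condition raises a second question, about who is randomized. If 3.2 governs, a subject consented and randomized before surgery enters the trial before anyone can know whether the condition is met. If 5.4.1 governs, the condition does not exist. Two members of staff following different sections could randomize different populations. Recruitment, randomization and retention are themselves feasibility objectives (1.2), so it also matters whether a subject lost between consent and Visit 1 counts as a randomized loss.

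**Working it through.** **1. Reading the Appendix.** Randomize is the 23rd column heading. The Screen and Consent entry has marks in columns 24-27 only (depression inventory, catheter removal, consent, chart review). The Baseline entry has a mark in column 23. Both entries line up with their labels. The Visit 2 and Visit 10 entries are displaced in the extracted text and are not used here.

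**2. Order of events under 6.2.** Let r be the post-operative day of catheter removal. Visit 1 is then day r+1 to r+2, taking 24-48 hours as the interval (5.5.1 says at least that).
- Consent on day -1 or 0: gap from assignment to baseline = r+1 to r+3 days. With r = 5 this is 6 to 8 days.
- Consent at removal: gap = 1 to 2 days.
- Single-shot block: no interval is given.

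In every catheter case the gap is positive, so assignment precedes baseline. The number of days does not measure bias; only the order matters.

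**3. Effect on the change score.** With mean baseline B and follow-up F, the difference in mean change is (F1 - B1) - (F2 - B2). Replacing B1 by B1 + b gives (F1 - B1) - (F2 - B2) - b. A shift of b points in one arm's mean baseline moves the comparison by exactly b points. Nothing in the documents allows b to be estimated. Raw scores and the monthly means in 6.3 contain no B and do not change through this route.

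**4. Is the pain condition applied anywhere else?** Sections 5.4.1, 5.4.2, 5.5 and 5.5.1 were compared with 3.2, and none applies it. The test stimulation in 5.5.2 checks whether pain responds to stimulation, and only in Group 1. Each subject randomized at consent who later lacks the pain named in 3.2 is 1/8 = 12.5% of an arm. How many there would be cannot be estimated.

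**5. Time left if randomization is at Visit 1.** Section 5.5.1 has leads placed by day 7. Time left = 7 - (r+2) to 7 - (r+1) = 5 - r to 6 - r. With r = 5 this is 0 to 1 day.

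**6. Consents needed if the pain condition is kept.** To randomize 16 when a share s does not qualify, 16/(1 - s) are needed:
- s = 10% (assumed): 16/0.9 = 17.8, so 18.
- s = 30% (assumed): 16/0.7 = 22.9, so 23.

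The study lasts 18-24 months and each subject takes part for about 12, leaving 18 - 12 = 6 to 24 - 12 = 12 months for accrual. The planned rate is 2-4 per month, taken here to apply to consents.

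| Consented | Months at 2 per month | Months at 4 per month | Rate needed for 6 months |
|---|---|---|---|
| 16 | 8 | 4 | 16/6 = 2.7 |
| 18 | 9 | 4.5 | 18/6 = 3.0 |
| 23 | 11.5 | 5.75 | 23/6 = 3.8 |

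Every case fits 12 months at any planned rate. A 6-month window needs the rates in the last column.

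**The case against.** The strongest reply is that 6.2 can be read as a sequence: consent, then at some later point randomization. An envelope is assigned, but the text does not say when it is opened or when the arm is disclosed. The groups part only after the Visit 1 assessment in 5.5.1, which fits opening at that visit. The subject flowchart (Figure 1) and the text between 5.6 and 6.0 were not available for this check and might show that order. This stands in part: bias is possible, not demonstrated. It does not rescue the wording of 6.2, which still needs correcting so that staff cannot open the envelope at consent.

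A second reply is that this is an openly unblinded pilot of 16 with unadjusted p-values, and later self-report stays unblinded whatever is done. That is true, and it limits the gain to the baseline. But the results are meant to refine randomization and assessment procedures for a larger trial, so their order is worth settling.

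A reader might also infer that the FIM comparison is biased in the same way. The documents do not support that: the baseline FIM is recorded with the help of Physical Therapy (4.2.6), and nothing makes it a self-report, so the mechanism above does not clearly reach it.

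**Conclusion.** The point holds in a limited form and should be fixed; confidence is medium. Section 6.2 and the Appendix give different times for randomization. Section 3.2 states a pain condition that no operative section applies and that cannot be observed at a pre-surgery consent.

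The possible bias affects the between-group comparison of changes in pain. It rests on two assumptions: that the arm is known when the envelope is assigned, and that Visit 1 is the reference for change. Its size is b points for a baseline shift of b, with b unknown. It would go too far to conclude that subjects do know their arm at baseline, or that the trial's pain results as a whole are biased: the documents do not state the first, and raw scores and monthly means need no baseline.

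**What to change.** 1. In 6.2 and the Appendix, state that the envelope is opened at Visit 1, only after eligibility is confirmed and all baseline forms are complete. State that the 16 are subjects randomized and that those consented but not randomized are reported separately. Section 5.5 uses *enrolled* for consent, while 8.2 leaves screen failures out of the enrolled number and 5.5.8 counts the 3, 6 and 12 month calls from enrollment. So also define the term and name the date that anchors those calls.
2. Reconcile 3.2 and 5.4.1 on whether moderate pain is required, with any cut-off set by the sponsor. If it is required, apply it to both groups before the envelope is opened.

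**Cost.** The edits are wording, but they have practical consequences.
- With catheter removal on day 5, only 0-1 day remains before the existing placement limit, so a placement slot must be held provisionally before the arm is known. Visit 1 already precedes placement, so the window itself is unchanged.
- If pain is required, more than 16 must be consented: 18 or 23 under the assumed shares. A 24-month study accommodates this at any planned rate. An 18-month study does so only at about 3 or 3.8 per month or more, where 16 already needs about 2.7.
- With blocks of two, staff can foresee the second assignment of each pair (8 of 16). An eligibility check just before opening could therefore be used selectively, so its result must be documented before the envelope is opened.
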